7.2 Patient Registration and Randomization and Dispensing of Study Drug

After the patient is determined to be eligible at the start of the screening period at Visit 1, the investigator or qualified designee will access the IRT to enroll the patient. Upon registration, the patient will be assigned a unique patient identification number.

At study sites with limited or no weekend hours, patients should be randomized on a Tuesday, Wednesday, Thursday, or Friday. It is recommended that study visits be scheduled in the morning, as multiple blood samples are required to be obtained over a period of several hours at Visit 4.

After final confirmation of eligibility at Visit 3, the investigator or qualified designee will access the IRT to randomize the patient and will obtain the patient identification number, as well as the code for the study drug wallet to be dispensed. At each subsequent visit during the treatment period when study drug is dispensed, the investigator or qualified designee will access the IRT to obtain the code for the study drug wallet to be dispensed. The investigator or qualified designee will record the code for the study drug wallet on the appropriate eCRF page at each visit during the treatment period.

A supply of study drug adequate for 1 week of treatment will be dispensed at Visit 3 and Visit 5, and a supply of study drug adequate for 2 weeks of treatment will be dispensed at Visit 4 (Section 5.6).

COVID-19—related Measure:

If it is anticipated that the patient will not be able to return to the study site after Visit 4, a supply of study drug adequate for the remaining 3 weeks of treatment may be dispensed to the patient at Visit 4.

Alternatively, if a patient is unable to return to the study site at Visit 4 or Visit 5, a supply of study drug adequate for all remaining weeks of treatment may be dispensed by the investigator or qualified designee and delivered via a site-to-patient delivery vendor (using a courier service) if locally available and if approved for use. Details, including contact information for the site-to-patient delivery vendor in each country, are specified in the Pharmacy Manual.

7.3 Eligibility Assessments

The screening period during which patient eligibility is determined may range in duration from 18 to 28 days. A screening period of a longer duration than 18 days (eg, 28 days) allows for repeating the cough count recording at Visit 1 if the Visit 1 recording initially fails and for repeating the cough count recording at Visit 2 if the Visit 2 recording initially fails (see Section 7.4.1).

Enrolled patients will be assessed versus the inclusion and exclusion criteria in the protocol (Section 4.2 and Section 4.3, respectively). As part of this assessment, patients will be given an eDiary at the start of the screening period at Visit 1 and instructed on its use and to record daily the average number of coughs per hour on the preceding day (ie, prior 24 hours) in the eDiary, starting from the day of Visit 1 and continuing up to the day of Visit 2.

Data entered by the patient in the eDiary will be automatically uploaded from the device to the database maintained by the device vendor. Procedures regarding the eDiary are specified in a separate document.

7.4 Efficacy Assessments

Efficacy assessment methods are described in Section 7.4, as well as presented in the Time and Events Schedule (Appendix 1).

Efficacy will be assessed based on cough monitor recordings of cough counts and questionnaires or instruments routinely used in studies in this patient population. The patient will complete these questionnaires and instruments in an electronic tablet and in an eDiary. At those visits at which questionnaires or instruments are required to be completed, completion by the patient is required prior to study site personnel conducting any other study procedures. Procedures regarding completion of these questionnaires and instruments, including the order of their administration at each visit, are specified in a separate document.

Data entered by the patient in the electronic tablet and eDiary will be automatically uploaded from the devices to the database maintained by the device vendor. Procedures regarding the electronic tablet and eDiary are specified in a separate document.

7.4.1 Number of Coughs (VitaloJAK™ Cough Monitor)

The number of coughs over a 24-hour period will be recorded at Visit 1, Visit 2, Visit 4, Visit 5, and Visit 6 with the VitaloJAKTM cough monitor [27]. This cough monitor has CE marking in the European Union and 510(k) approval from the United States Food and Drug Administration (FDA).

The cough monitor will be applied to the patient at each of these visits, and the patient will be instructed to remove the monitor after 24 hours. Instructions for the application of the cough monitor to the patient are specified in a separate document.

If, based on initial assessment at the study site, the cough count recording at Visit 1 or Visit 2 is considered to have failed for any reason, the recording may be repeated (see details for Visit 1 in Section 8.1 and for Visit 2 in Section 8.3). Repeat recording of the cough count is not permitted at any other visits in the study.

Data collected with the cough monitor will be sent from the study site to the cough monitor analysis institution via the web portal of that institution. The number of coughs will be measured (including classification of awake and asleep hours) by cough analysis technicians for each of the following periods:

- 24 hours
- Waking hours
- Sleeping hours

The number of coughs will be reported by the cough monitor analysis institution to the sponsor, with counts provided for each 24-hour period and for the waking hours and the sleeping hours within each 24-hour period. Procedures regarding the cough monitor analysis are specified in a separate document.

7.4.2 Cough Severity as Assessed on the Visual Analog Scale (VAS)

7.4.2.1 Weekly Severity of Cough (Electronic Tablet)

The patient will be asked to provide his/her assessment of the severity of cough during the past week at Visit 1, Visit 2, Visit 4, Visit 5, and Visit 6 and/or, if applicable, at the time of discontinuation of study drug on the VAS using the electronic tablet.

Data collected with the electronic tablet will be automatically uploaded from the device to the database maintained by the device vendor. Procedures regarding the electronic tablet are specified in a separate document.

7.4.2.2 Daily Severity of Cough (eDiary)

The patient will be instructed to record daily the severity of cough on the preceding day (ie, prior 24 hours) on the VAS in the eDiary, starting at Visit 1 and continuing up to Visit 4 (ie, through Day 7) and/or, if applicable, at the time of discontinuation of study drug.

Data collected with the eDiary will be automatically uploaded from the device to the database maintained by the device vendor. Procedures regarding the eDiary are specified in a separate document.

7.4.3 Leicester Cough Questionnaire (LCQ) (Electronic Tablet)

The LCQ is a patient-reported QOL measure of chronic cough [28]. The questionnaire consists of 19 items to which the patient responds on a 7-point Likert response scale. Each item assesses symptoms during cough and the effect of cough on 3 main domains: physical, psychological and social. The LCQ generally takes about 5 minutes to complete.

The patient will be asked to complete the LCQ at Visit 1, Visit 2, Visit 4, Visit 5, and Visit 6 and/or, if applicable, at the time of discontinuation of study drug using the electronic tablet [28].

Data collected with the electronic tablet will be automatically uploaded from the device to the database maintained by the device vendor. Procedures regarding the electronic tablet are specified in a separate document.

7.4.4 International Consultation on Incontinence Questionnaire Short Form (ICIQ-SF) (Electronic Tablet)

The ICIQ-SF is a patient-reported measure of the severity of urinary incontinence and QOL for those with urinary incontinence [29]. The questionnaire consists of 4 items that evaluate the frequency, severity, and impact of urinary incontinence on QOL. The ICIQ-SF takes a few minutes to complete.

The patient will be asked to complete the ICIQ-SF at Visit 2 and Visit 6 and/or, if applicable, at the time of discontinuation of study drug using the electronic tablet.

Data collected with the electronic tablet will be automatically uploaded from the device to the database maintained by the device vendor. Procedures regarding the electronic tablet are specified in a separate document.

7.4.5 Short Form (36) Health Survey (SF-36) (Electronic Tablet)

The SF-36 is a patient-reported measure of overall health status. The questionnaire consists of 8 scaled scores (health concepts) and evaluates vitality, physical functioning, bodily pain, general health perceptions, physical role functioning, emotional role functioning, social role functioning, and mental health. Scores for each scale range from 0 to 100; the lower the score, the greater the disability [30]. The SF-36 takes approximately 5 to 10 minutes to complete [31].

The patient will be asked to complete the SF-36 at Visit 2 and Visit 6 and/or, if applicable, the Early Discontinuation Visit using the electronic tablet.

Data collected with the electronic tablet will be automatically uploaded from the device to the database maintained by the device vendor. Procedures regarding the electronic tablet are specified in a separate document.

7.4.6 Patient Global Impression of Change (PGIC) (Electronic Tablet)

The PGIC is a patient-reported measure of overall health status and consists of one item adapted from the Clinical Global Impressions scale [32].

The patient will be asked to complete the PGIC at Visit 6 or, if applicable, the Early Discontinuation Visit using the electronic tablet.

Data collected with the electronic tablet will be automatically uploaded from the device to the database maintained by the device vendor. Procedures regarding the electronic tablet are specified in a separate document.

7.5 Pharmacokinetics Assessments

All patients will have blood samples collected for measurement of plasma concentrations of S-600918 and its metabolite (S-600918 acyl glucuronide) at Visit 4 and Visit 6, and/or, if applicable, at the time of discontinuation of study drug.

At Visit 4, the patient is not to take study drug until after arrival at the study site; at Visit 6, the patient is permitted to take study drug before arrival at the study site (Section 5.3).

At Visit 4, three blood samples will be collected. The first blood sample will be collected after patient completion of specified questionnaires and instruments prior to the patient taking the dose of study drug that day. The dose of study drug will then be taken, and then the second and third blood samples will be collected 1 hour and 2 hours after the dose of study drug. If the patient inadvertently takes the dose of study drug before coming to the study site on the day of Visit 4, a blood sample will be collected after patient completion of specified questionnaires and instruments and then again 1 hour and 2 hours after collection of the first blood sample.

At Visit 6, a blood sample will be collected after patient completion of specified questionnaires and instruments.

The blood will be collected in a tube containing an anticoagulant (heparin sodium) and immediately centrifuged. Centrifuged plasma will be separately dispensed into polypropylene tubes and frozen and stored below -20° C. Samples will be shipped under freezing conditions with dry ice to the laboratory. Instructions for sample collection, handling, and shipment are provided separately.

COVID-19–related Measure:

In the event a visiting nurse service is used at Visit 4, Visit 6, and/or the Early Discontinuation Visit (if applicable) as described in Section 8, refer to the separate document for directions regarding handling and shipping of blood samples for PK analysis.

The investigator or qualified designee will record the date and time the blood samples were obtained on the appropriate eCRF page.

7.6 Safety Assessments

Safety assessment methods are described in Section 7.6, as well as presented in the Time and Events Schedule (Appendix 1).

7.6.1 Physical Examinations

A complete physical examination (including measurement of height [in centimeters] and body weight [in kilograms]) will be performed by the investigator or qualified designee at Visit 1. An abbreviated physical examination (limited to the respiratory system) will be performed at Visit 2, Visit 3, Visit 4, Visit 6, and Visit 7, and/or, if applicable, the Early Discontinuation Visit.

The investigator or qualified designee will record the date of the complete and abbreviated physical examinations and whether the physical examination is normal, abnormal but not clinically significant, or abnormal and clinically significant on the appropriate eCRF page. At Visit 1 only, the measurements of height and weight will also be recorded on the appropriate eCRF page. The investigator or qualified designee also will record clinically significant changes as adverse events on the appropriate eCRF page.

7.6.2 Clinical Laboratory Tests

7.6.2.1 Routine Laboratory Tests

The investigator or qualified designee will collect blood and urine samples for the routine laboratory tests shown in Table 7-1 at Visit 1, Visit 2, Visit 4, Visit 6, and Visit 7, and/or, if applicable, the Early Discontinuation Visit.

Blood samples for the routine laboratory tests will be collected in the fasting state at Visit 1 only; patients will be required to fast for 12 hours prior to blood sample collection. For sample collection subsequent to Visit 1, fasting is not required. Patients will be in a seated position during blood collection.

Table 7-1 Routine Laboratory Tests

Test	Analyte
Hematology	Hematocrit, hemoglobin, platelet count, erythrocytes (red blood cells), and leukocytes (white blood cells) with differential (eosinophil count, basophil count, neutrophil count, monocyte count, and lymphocyte count)
Blood chemistry	ALP, ALT, AST, total bilirubin, GGT, lactate dehydrogenase, blood urea nitrogen, creatinine, sodium, potassium, chloride, calcium, glucose, total protein, uric acid, total cholesterol, and creatine phosphokinase
Urinalysis	Glucose, occult blood, protein, and urobilinogen

ALP = alkaline phosphatase; ALT = alanine aminotransferase; AST = aspartate aminotransferase; GGT = gamma glutamyl transferase.

The investigator will determine whether abnormal changes are clinically significant (Section 7.6.5.6), and record any clinically significant changes as adverse events on the appropriate eCRF page.

The investigator or qualified designee will record the date of sample collection for routine laboratory tests on the appropriate eCRF page.

7.6.2.2 Additional Tests

A blood sample will be obtained at Visit 1 for testing for HIV antigen, HIV antibody, hepatitis B virus surface antigen, and hepatitis C virus antibody. For patients with a positive result for hepatitis C virus antibody, the blood sample also will be tested for hepatitis C virus RNA.

For female patients who have not been identified to be postmenopausal (defined as at least 12 months of spontaneous amenorrhea in women >45 years of age) or surgically sterile by hysterectomy, bilateral oophorectomy, and/or bilateral salpingectomy or tubal ligation with appropriate documentation of such surgery, a urine pregnancy test will be performed at Visit 1, Visit 2, Visit 6, and Visit 7 and/or, if applicable, the Early Discontinuation Visit.

The investigator or qualified designee will record the date of sample collection at the specified visit(s) (as applicable) on the appropriate eCRF page.

7.6.2.3 Sample Collection, Storage, and Shipping

Blood and urine samples will be collected at specified observation points by the investigator or qualified designee. All samples except urine samples for pregnancy testing will be sent to the central laboratory for processing. Urine samples for pregnancy testing should be tested at the study site or sent to the local laboratory for testing. Procedures for sample collection, handling, labeling, storage, and shipping are specified in the Laboratory Manual.

COVID-19—related Measure:

In the event a visiting nurse service is used at Visit 4, Visit 5, Visit 6, Visit 7, and/or the Early Discontinuation Visit (if applicable) as described in Section 8, refer to the separate document for directions regarding handling and shipping of blood and urine samples for analysis.

7.6.3 Blood Pressure and Pulse Rate

The investigator or qualified designee will measure systolic and diastolic blood pressure and pulse rate at Visit 1, Visit 2, Visit 3, Visit 4, Visit 5, Visit 6, and Visit 7 and/or, if applicable, the Early Discontinuation Visit. Blood pressure and pulse rate will be measured after the patient has been in a sitting position for approximately 3 minutes.

The investigator or qualified designee will record the date of these measurements and the blood pressure and pulse rate measurements at each of these visits on the appropriate eCRF page. The investigator or qualified designee also will record clinically significant changes as adverse events on the appropriate eCRF page (Section 7.6.5.6).

7.6.4 Electrocardiograms

The investigator or qualified designee will perform a standard 12-lead ECG at Visit 1, Visit 2, Visit 6, and Visit 7, and/or, if applicable, the Early Discontinuation Visit. The

ECG will be performed after the patient has been in a recumbent or semi-recumbent position for approximately 3 minutes.

The investigator or qualified designee will assess whether the ECG is normal or abnormal and, if considered abnormal, whether the ECG finding(s) is(are) clinically significant and, if clinically significant, whether related to medical history. Abnormal ECG findings considered to demonstrate a clinically significant change will be recorded as adverse events on the appropriate eCRF page (Section 7.6.5.6).

The investigator or qualified designee will record the date of the ECG at each of these visits, along with the assessment of whether the ECG was normal, abnormal but not clinically significant, or abnormal and clinically significant and, if applicable, relevant medical history on the appropriate eCRF page.

7.6.5 Adverse Events Assessment

7.6.5.1 Definition and Assessment of Adverse Events

An adverse event is defined as any untoward medical occurrence in a patient administered a pharmaceutical product (including investigational drug) during the course of a clinical investigation. An adverse event can therefore be any unfavorable and unintended sign (including an abnormal laboratory finding), symptom, or disease temporally associated with the use of an investigational product, whether or not considered related to the investigational product. An elective procedure not reflecting a worsening of a known underlying medical condition is not considered an adverse event, and therefore will not be considered an SAE despite requiring hospitalization. However, complications of a procedure will be considered an adverse event and may be considered an SAE if hospitalization is prolonged (or any other SAE criterion is met). A hospitalization or prolongation of a hospitalization for reasons other than an adverse event would not be considered an SAE.

Adverse events include events that are new in onset, as well as events that are present at Visit 1 and increase in severity or frequency during the study and medical conditions that are present at Visit 1 and worsen during the study. In addition, adverse events include abnormal results of study procedures (eg, physical examinations, laboratory tests, measurements of blood pressure and pulse rate, and ECGs) that are considered by the investigator or qualified designee to be clinically significant.

The investigator or qualified designee is responsible for identifying adverse events. Adverse events may be identified based on the patient's spontaneous report or based on non-leading questions by the investigator or qualified designee, physical examinations, laboratory tests, blood pressure and pulse rate measurements, and ECGs.

The investigator or qualified designee is responsible for fully investigating and recording the following information about adverse events on the appropriate eCRF page: period of onset (screening period, treatment period, or follow-up period), start date, end date (if an outcome is reported as recovered/resolved or fatal), severity, seriousness with the reason

for considering the adverse event to be serious, relationship to the study drug, action

for considering the adverse event to be serious, relationship to the study drug, action taken to manage the adverse event, and outcome of the adverse event.

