3.3 Study Duration

3.3.1 Study Duration in Individual Patients

The study duration for each patient is approximately 8 to 10 weeks (screening, 18 to 28 days; treatment, 28 days; and follow-up, 14 days).

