7.6.5.2 Assessment Period

Adverse events will be collected from the date of signing the informed consent form through Visit 7 (or 14 days after the date of the last dose of study drug if study drug was discontinued). If a patient withdraws from the study, the investigator or qualified designee will make every effort to collect adverse events for 14 days after the last dose of study drug.

Any adverse event considered to be related to study drug that is ongoing 14 days after the last dose of study drug and any SAE regardless of relationship to study drug that is ongoing 14 days after the last dose of study drug will be followed until resolution, until it is judged by the investigator or qualified designee to have stabilized or become chronic, or until the patient is lost to follow-up.

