9.12 Safety Analyses

9.12.1 Adverse Events

Adverse events will be classified by system organ class and preferred term using Medical Dictionary for Regulatory Activities (MedDRA). Adverse events reported after the initial dose of study drug will be considered TEAEs and will be analyzed.

The number and percentage of patients with at least 1 TEAE, fatal and nonfatal treatment-emergent SAEs, and TEAEs leading to discontinuation of study drug will be summarized by treatment group. The percentages of patients in these TEAE categories and the 95% confidence intervals will be calculated by using the Clopper-Pearson method. The number and percentage of TEAEs will also be presented. Treatment-related TEAEs will be summarized in the same manner as TEAEs.

The number and percentage of patients with TEAEs will be summarized by MedDRA system organ class and preferred term for each treatment group. The number and percentage of patients with TEAEs by severity and outcome will be presented by MedDRA system organ class and preferred term for each treatment group.

The number and percentage of patients with an adverse event that reflects taste change as defined using the Standardized MedDRA Query (SMQ) category of "Taste and smell disorders" will be summarized by preferred term for each treatment group. Responses to the taste questionnaire will be summarized descriptively.

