9.1. Adverse Events

Treatment Emergent Adverse Events (TEAEs) will be defined as an adverse event that may have an onset following administration of study drug. For the purposes of classifying adverse events according to this definition, events with partial onset dates will be considered as the closest possible date to the last day of study drug dosing. In general, summaries will be provided by treatment group, and by MedDRA system organ class (SOC) and preferred term (PT).

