9.1.1. Incidence of Adverse Events

An overall summary of TEAEs will be presented by treatment group and will include the number and percentage of patients with at least one TEAE, any serious TEAEs, any fatal TEAEs, and any TEAEs leading to discontinuation of study drug. The 95% confidence intervals for these percentages by the Clopper-Pearson method will be presented. Similarly, the number of patients experiencing these events will be compared at each level of active S-600918 dosing to placebo using Fisher's exact test.

The number and percentage of patients with TEAEs will be summarized by SOC and PT for each treatment. All AEs will be presented in a listing.

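### SAP 9.1 dates partially dated adverse events without using the recorded period of onset, so, read literally, some events recorded as starting in screening become treatment-emergent

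*Protocol*

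**What the plan says.** **What is collected.** Protocol 7.6.5.2 starts collection before dosing: "Adverse events will be collected from the date of signing the informed consent form through Visit 7". Events from the screening weeks are therefore in the database. For each event, Protocol 7.6.5.1 lists "period of onset (screening period, treatment period, or follow-up period), start date, end date" among the items to be recorded on the eCRF. The period is a field of its own and does not depend on the start date being complete.

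**How status is decided.** Protocol 9.12.1 says: "Adverse events reported after the initial dose of study drug will be considered TEAEs and will be analyzed". It has no rule for incomplete dates. SAP 9.1 defines a TEAE as "an adverse event that may have an onset following administration of study drug" and adds, for classifying events under that definition, that "events with partial onset dates will be considered as the closest possible date to the last day of study drug dosing". SAP 9.1 neither uses the period of onset nor rules it out.

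**Where status is used.** The overall TEAE counts carry Clopper-Pearson intervals and are "compared at each level of active S-600918 dosing to placebo using Fisher's exact test" (SAP 9.1.1). Status also determines the tables by severity, seriousness and discontinuation (SAP 9.1.3 to 9.1.5), the relative-risk forest plots by region (9.1.7) and the taste tables (9.1.8).

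**The concern.** Leaning towards treatment is a sound convention when the timing of an event is unknown. Here the trial may already know that the event began before dosing, because the investigator has recorded it as a screening event, yet the written rule looks only at the known part of the date. The same event with a complete pre-dose date would not be a TEAE. With the day missing it can become one.

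At stake is a little noise in the safety tables. Events that began before dosing cannot be effects of the drug. Counted as TEAEs, they raise the rates in every arm and pull relative risks against placebo towards one. The overall row (patients with at least one TEAE) changes only for a patient with no other TEAE. A single added case shows most in a sparse row of the SOC and preferred-term tables.

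The gap also affects reproducibility. Two programmers following SAP 9.1, one reading the period field and one not, could produce different TEAE tables.

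**Working it through.** The documents give no figure for this rule, so there is none to reproduce. The check applies the SAP 9.1 rule to calendar dates.

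**Inputs.** Period lengths are from Protocol 3.3.1: "screening, 18 to 28 days; treatment, 28 days; and follow-up, 14 days". Assumptions:
- Last dose is on Day 28.
- First dose is equally likely on each of the 366 days of 2020.
- True onset is equally likely on each of the L days before first dose.
- An assigned date of Day 1 or later counts as a TEAE.

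**The rule.** Let the known part of the date allow the range from lo to hi. The possible date closest to the last dose is min(max(last dose, lo), hi).

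**Worked example.** First dose 20 March 2020, last dose 16 April 2020 (Day 28).

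| Recorded period | Known date | Range | Assigned date | TEAE? |
|---|---|---|---|---|
| Screening | ?? March | 1–31 March | 31 March | Yes, against the recorded period |
| Screening | ?? February | 1–29 February | 29 February | No |
| Follow-up | ?? April | 1–30 April | 16 April | Yes |

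In the first row, letting the recorded period limit the range leaves 1–19 March. The assigned date becomes 19 March and the event is not a TEAE.

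**Share affected, day missing.** The assigned date reaches Day 1 exactly when onset and first dose fall in the same calendar month. If first dose is on day m of a month, min(m − 1, L) of the L possible onset days lie in that month. Summing over m:

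| Month length | Months in 2020 | Sum, L = 18 | Sum, L = 28 |
|---|---|---|---|
| 31 | 7 | 171 + 12×18 = 387 | 406 + 2×28 = 462 |
| 30 | 4 | 171 + 11×18 = 369 | 406 + 1×28 = 434 |
| 29 | 1 | 171 + 10×18 = 351 | 406 |

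Here 171 = 0 + 1 + … + 18 and 406 = 0 + 1 + … + 28.

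- L = 18: (7×387 + 4×369 + 351) / (366×18) = 4536 / 6588 = 0.689.
- L = 28: (7×462 + 4×434 + 406) / (366×28) = 5376 / 10248 = 0.525.

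A day-by-day enumeration gives the same two values, and a separate simulation agrees to within 0.001.

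**Share affected, day and month missing.** The event escapes only if onset fell in the previous calendar year: 171 / 6588 = 0.026 for L = 18 and 406 / 10248 = 0.040 for L = 28. The shares counted as TEAEs are therefore 97.4% and 96.0%.

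**After the fix.** The share is 0% in both cases, provided the recorded period is consistent with the known part of the date.

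The denominator throughout is screening-onset events with partial dates in patients who were later dosed. It is not all adverse events.

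**The case against.** The strongest reply is that the SAP does not tell anyone to override the field. It asks for the closest possible date, and for events that may have begun after dosing. An event recorded as a screening event arguably has no possible post-dose date, so a careful programmer would reach the right answer. This stands as far as it goes: a reader might infer that the plan instructs analysts to count known pre-dose events, and the text does not support that. What remains is that SAP 9.1 does not state the limit, and the literal date-only reading gives the wrong class.

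Second, such events should be rare. Screening lasts 18 to 28 days, adverse events are recorded at Visits 1, 2 and 3 (Protocol 8.1 to 8.3), and eCRF entries are queried for completeness (Protocol 10.7.1). Patients who fail screening never enter the safety population. A year-only date for an event of the past four weeks is hard to imagine. All of this stands.

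Third, leaning towards treatment is cautious, and the same rule applies to every arm. That is right, and no bias favouring one arm is shown. Caution of this kind is not needed, however, where pre-dose onset is already on record.

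Fourth, the period field does not prove post-dose onset in the other direction. The treatment period begins on Day 1 (Protocol Appendix 1), and Protocol 8.3 lists adverse event recording before randomization and first dose. A pre-dose event on Day 1 could therefore be labelled as treatment period. This stands and narrows the fix: only the screening label settles the matter.

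**Conclusion.** The point holds as a small gap in specification. SAP 9.1 classifies partial onset dates without using the recorded period of onset. Taken literally, it turns about 52% to 69% of screening-onset events with a missing day into TEAEs, under uniform onset and uniform first-dose dates. The number of such events is not in the documents and is probably very small, possibly zero. Complete dates are unaffected.

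Three stronger readings are not supported:
- **That this is a latest-date rule.** It gives the latest possible date only when the range ends on or before the last dose. Otherwise it gives the last dosing day or, if the range starts later, the earliest possible date, as the follow-up row of the example shows.
- **That the treatment-related tables are distorted.** Protocol 7.6.5.4 reserves that rating for events reasonably explained by study drug, and an event recorded as starting in screening should not carry it.
- **That the comparison tilts towards a dose.** The added events fall on all arms alike and would mainly dilute the contrast with placebo.

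This is a minor clarification, worth making because it is cheap and removes an ambiguity before unblinding.

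**What to change.** Add one sentence to SAP 9.1: before the closest-date rule is applied to a partial onset date, the possible dates are limited by the recorded period of onset and by any end date that precedes the first dose, so that a partially dated event recorded in the screening period is not a TEAE.

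Keep the present rule unchanged for events recorded in the treatment or follow-up period, and where the period is missing or contradicts the known part of the date. Do not make the treatment-period label sufficient for TEAE status, because that period includes the pre-dose part of Day 1.

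The cost is one sentence and one condition in the derivation program. The field is already collected, so neither the eCRF nor the protocol needs to change. A listing of events with partial onset dates, showing recorded period and derived status, would let a reader confirm how few are affected.
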